3.2 Diagnostic work-up before randomization

3.2.1 Body temperature measurement and nucleic acid test

For safety reasons, we conducted nucleic acid test and body temperature test for each patient undergoing MCE before entering the examination room.

3.2.2 Informed consent

The principles of informed consent in the current edition of the Declaration of Helsinki will be implemented. Written informed consent will be obtained from patients before inclusion in the trial.

The investigator must introduce this study in detail to the patients, including content, purpose, intended efficacy, possible AEs, and countermeasures before signed the informed consent and patients will be given as much time as they need to make a decision.

The informed consent form shall be signed jointly by the investigator and the patient. It is in duplicate, and each party maintains one copy.

CHAPTER 4: INTERVENTIONS AND OUTCOMES

4.1 MCE system and ncMCE system

The MCE system (Ankon Technologies Co., Ltd. Shanghai, China) consists of a guidance C-arm magnet robot, a computer workstation with ESNavi software, endoscopic capsule, capsule locator, and a vest-like data recorder that can receive capsule signal from both sides [12]. The ncMCE system adds a remote control workstation and an audio-visual exchange system to the original well-established MCE system, which was developed and tested at our medical center [10]. To simplify the preparation process, we embedded the data recorder in the examination bed. The ncMCE system separates endoscopist and patients in two rooms (control room for endoscopist and examination room for patients), offering physical isolation for noninvasive gastric examination during the pandemic [11].

4.2 Study intervention

- Patients were required to report personal history and have chest computed tomography or nucleic acid testing to exclude COVID-19 infection within 3 days before their examination. Patients who are confirmed to have a COVID-19 infection and symptoms of pneumonia should be treated at special medical institutions first. Only when this population needs immediate endoscopy should those procedures be done in specific wards that have COVID-19 infection prevention protocols in place [13]. On arrival at the hospital in the morning after an overnight fast (> 8 hours), each patient took a 400-mg simethicone suspension dissolved in 100 mL water 40 minutes before they ingested the capsule ingestion according to standardized gastric preparation [14]. Another 800 to 1000 mL of water could be taken 10 minutes before capsule ingestion to distend the stomach [12]. Then, a patient's hands were disinfected and they were given the data recorder after entering the examination room. Next, a patient laid down on the examination bed next to the computer workstation, assumed the supine or left-lateral decubitus position, and swallowed the capsule, which had already been activated. An endoscopist controlled capsule movement with the help of a magnet robot using two joysticks in front of the workstation or automatically using a default mode. To ensure that the gastric mucosa was completely visualized, the endoscopist directed a patient to change position to supine and right-lateral decubitus. In the ncMCE group, a patient and the endoscopist entered two rooms through different routes and gastric preparation was under the remote guidance [15]. The audio-visual exchange system provided a platform for the endoscopist to see and communicate with a patient during examination. The data recorder was embedded in the examination bed to avoid cross-infection of COVID-19 among patients and simplify the disinfection process. Enhanced personal protective equipment (PPE) including an N95 mask, isolation gown with water resistance, head cover, eye protection, and face shield [11] should be worn by medical staff in the capsule endoscopy examination room when performing MCE. The steps for donning and doffing PPE were strictly followed, according to the standard process [16]. Medical masks were used as basic PPE for endoscopists in the ncMCE group (Supplementary material, Table 1) [17]. After each examination, the returned data recorder was disinfected using ultraviolet light, 75% alcohol, or ethylene oxide and the sheets on the bed were replaced.

4.3 Study outcomes

4.3.1 Primary efficacy outcome

The primary endpoints were feasibility assessed by completion rate (CR) and safety evaluated by the occurrence of AE. CR was defined as complete observation of the cardia, fundus, body, angulus, antrum, and pylorus of the stomach with no technical failure. Technical failure included incomplete observation, direct contact in the ncMCE group, and examination discontinuation. The safety of ncMCE was evaluated 2 weeks after the procedure for any AEs, such as infection with SARS-CoV-2 and capsule-related AEs including abdominal pain, nausea, vomiting, and capsule impaction or retention. In the current study, the endoscopist was continuously monitored for infection until 2 weeks after the last examination.

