2.1 Introduction and rationale

COVID-19, a respiratory disease that spreads via direct contact or through droplet transmission, has caused a major disruption in the healthcare system since it was first identified in 2019 [1]. Endoscopic procedures during the pandemic were divided into urgent endoscopy, semi-urgent endoscopy, and elective endoscopy, with the aim of preventing infection among healthcare professionals and providing necessary medical services [2]. For patients who required urgent gastroscopy, the face-to-face contact with endoscopists, aggressive suctioning, and coughing [3] during examination brought opportunities for transmission. Considering the reduced endoscopy volume in most endoscopy departments, diagnosis of patients who needed semi-urgent endoscopy and elective endoscopy may have been delayed [4]. Therefore, focusing on how to return to gradually return to provision of routine endoscopy services while maintaining safety for endoscopists deserves attention [5]. Capsule endoscopy provides a great view of the gastrointestinal tract through use of a miniature, pill-sized camera and it is as accurate as other gastrointestinal endoscopy modalities [6]. Its unique advantages include single use, excellent tolerance, and minimal medical staff requirement, which reduces the risk of exposure to pathogenic microorganisms and cross-infection [7] and makes it an appropriate method for examining and triaging an endoscopy department during the COVID-19 pandemic [8]. However, capsule endoscopy cannot be used to avoid face-to-face contact between endoscopists and patients who have asymptomatic COVID-19 cases [9]. Herein, we describe a novel noncontact magnetically controlled capsule endoscopy (ncMCE) system using a remote control system to separate endoscopists and patients physically, which was developed and tested in our medical center [10,11]. The objective of the present study was to evaluate the feasibility and safety of ncMCE for gastric examination.

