5.2 Data collection

Information on the basic characteristics of the enrolled patients was collected prospectively. Each patient was followed up for 2 weeks by telephone and hospital information system to confirm capsule excretion and any adverse events (AEs), including COVID-19 infection. The maneuverability questionnaire for the endoscopist and improved questionnaire on pre-procedure perception and post-procedure satisfaction for patients were completed after the examination. To avoid systematic bias, a single endoscopist ([name]) performed each examination and made the diagnoses for all enrolled patients immediately. The evaluation of completion was made by another blinded researcher ([name]).

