6.1.2 Recording

All AEs reported by the patients or discovered from Electronic Medical Record were assessed for severity and relationship with study treatment by the investigators, with appropriate measures taken in time and detailedly documented.

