6.4 Relationship determination

The reporting investigator will complete the SAE report in the CRFs, including date of event, admissions, diagnosis details, date of discharge, whether result in the experiment and its sequela. Researchers should give targeted treatment and follow-up to AEs until symptoms disappear or remain stable.

Any adverse event should be judged on the basis according to the following criteria:

Irrelevant: There was no correlation between AE and the use of ncMCE .

possibly irrelevant: The occurrence of AE is more likely to be related to other factors, such as combination of drugs or accompanying diseases, or the occurrence time of AE indicates that it is unlikely to have a causal relationship with ncMCE .

Possibly relevant: AE may be caused by the use of ncMCE . There is a reasonable time sequence for the occurrence of incidents and the use of research-related devices and can exclude the effect of concomitant treatment and combined medication.

Affirmative relevant: The type of adverse event has been identified as a side effect of ncMCE and cannot be explained by other reasons. The occurrence order of the event strongly suggests causality.

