7.5 Protocol amendments

Before clinical investigation, the CIP will be discussed and revised jointly by investigators and implementers who will sign the final copy and submit it to the ethics committee for approval before implementation.

If there is a problem with the CIP during practical implementation of the clinical investigation, a revision is necessary. The plan of revision shall be proposed to the implementer for a multi-center discussion. After then, the responsible unit will carry out revision and submit the revised CIP in a written form to the implementer and investigation units for signing. Finally, send it to the ethics committee again for approval before implementation.

If new data important related to the product for verification is found, the informed consent form must be modified and sent to the ethics committee for approval.

CHAPTER 8: STATISTICAL CONSIDERATIONS

As a pilot study to evaluate the feasibility and safety of ncMCE, the sample size was not calculated [19]. Considering the capsule endoscopy volume of Shanghai Hospital during the pandemic, we planned to recruit 40 patients into two groups. Basic characteristics were presented as means with standard deviations for continuous variables such as age, body mass index (BMI), and percentages for binary variables including sex, medical history, and symptoms. Quantitative data were summarized with parametric statistics, mean and standard deviation, or nonparametric statistics, median, and interquartile range (IQR), whereas categorical data were presented as Under the condition of normal distribution and homogeneity of variance, variance analysis was used to compare the difference in mean between groups, while a K-W test was used to compare the difference in distribution between groups and Fisher' s test was used to compare the two and disordered multi-classification data of subjects under the condition that homogeneity of variance was not satisfied. All reported Pvalues are two-sided and differences that reached $P < 0.05$ were considered statistically significant. Statistical analyses were performed with SPSS (version 22.0, SPSS Inc., Chicago, Illinois, United States).

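### Two definitions treat the arms differently: Section 6.4 grades AE causality against ncMCE only, and completion rate counts direct contact as a failure in ncMCE only

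*Combined protocol and SAP*

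**What the plan says.** **Causality.** Section 6.4 asks for every AE to be graded on four levels, and each level is defined by its link to ncMCE. The highest requires that "The type of adverse event has been identified as a side effect of ncMCE". MCE is not named at any level. The only device-neutral words are in the timing condition of the third level: "There is a reasonable time sequence for the occurrence of incidents and the use of research-related devices". Elsewhere the scope is wider. The AE definition in Section 6.1.1.1 takes in events linked to the control device, and Section 6.1.2 has all AEs "assessed for severity and relationship with study treatment by the investigators".

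**Completion rate.** CR is a primary endpoint (Section 4.3.1). It requires all six gastric landmarks to be seen without technical failure, and "Technical failure included incomplete observation, direct contact in the ncMCE group, and examination discontinuation". Incomplete observation and discontinuation apply to both arms; contact applies to one. Appendix 1 shows that MCE has no physical isolation, so it has no equivalent failure.

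**Objective and analysis.** Section 2.1 states: "The objective of the present study was to evaluate the feasibility and safety of ncMCE for gastric examination". Chapter 8 says "we planned to recruit 40 patients into two groups", without a sample size calculation, and Section 3.1 randomises them 1:1. Chapter 8 also gives a general rule that Fisher's test "was used to compare the two and disordered multi-classification data of subjects". It neither names CR nor exempts it.

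**The concern.** Both arms swallow a magnetically guided capsule (Appendix 1), so capsule-related events can occur in either. If assessors follow Section 6.4 as worded, related AEs in MCE patients fall into the two unrelated grades. A table of related AEs by arm would then be one-sided by construction. Safety is co-primary, so the grading should work in both arms.

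For CR, one number would answer two questions: whether remote control images the stomach as well as MCE, and whether contact was avoided. In a between-arm comparison, a low ncMCE figure would not show which of the two failed.

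**Working it through.** **Part 1: causality, by comparison of sections.** Take an MCE patient whose AE was caused by the MCE examination.

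- The top grade needs an established side effect of ncMCE. Not met.
- The third grade needs the AE to be possibly caused by ncMCE. Not met. Its timing condition is device-neutral but only adds to that requirement.
- That leaves the two grades that deny or doubt a link with ncMCE. Both would be literally true.

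The literal count of related AEs in the MCE arm is therefore 0, whatever happens. Sections 6.1.1.1 and 6.1.2 imply the opposite intention. The primary endpoint counts AEs without regard to causality, so it does not change.

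**Part 2: completion rate.** The plan has no figure to reproduce.

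Inputs from the plan: 40 patients at 1:1, so 40/2 = 20 per arm; two-sided 0.05; Fisher's test. Assumed, because the plan gives neither: imaging completeness *c*, equal in both arms (90-100%), and ncMCE contact rate *r*.

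*Step 1. Cost of one contact in an otherwise complete examination:* 1/20 = 5 points.

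*Step 2. Contacts needed for P<0.05*, all falling in examinations with complete imaging:

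- 20/20 complete in each arm: 1 to 5 contacts give P = 1.000, 0.487, 0.231, 0.106, 0.047. Five are needed (15/20 v 20/20).
- 19/20 complete in each arm: 5 contacts give 0.092 and 6 give 0.044. Six are needed.
- 18/20 complete in each arm: 6 contacts give 0.065 and 7 give 0.031. Seven are needed.

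*Step 3. How often this would happen.* MCE success is *c*. ncMCE success is *c*(1-*r*) if contact is independent of imaging, min(*c*, 1-*r*) if contacts fall first in incomplete examinations (full overlap), and *c*-*r* if they fall only in complete ones (no overlap). Every pair of binomial outcomes was enumerated and its probability summed where Fisher's P<0.05, and again where ncMCE was at least 2/20 = 10 points lower. At *r* = 10%:

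| *c* | Overlap | ncMCE CR | Chance of P<0.05 | Chance of a gap of at least 10 points |
|---|---|---|---|---|
| 1.00 | all three alike | 0.900 | 0.0432 | 0.6083 |
| 0.95 | full | 0.900 | 0.0167 | 0.3678 |
| 0.95 | independent | 0.855 | 0.0623 | 0.5770 |
| 0.95 | none | 0.850 | 0.0696 | 0.5977 |
| 0.90 | full | 0.900 | 0.0118 | 0.2084 |
| 0.90 | independent | 0.810 | 0.0616 | 0.5515 |
| 0.90 | none | 0.800 | 0.0725 | 0.5866 |

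With no contact, for *c* = 1.00, 0.95 and 0.90, the chance of P<0.05 is 0, 0.0019 and 0.0118, and the chance of the gap is 0, 0.1263 and 0.2084. Across the same scenarios the chance of P<0.05 is 0.2-2.9% at *r* = 5% and 7-37% at *r* = 20%.

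*Step 4. A case these scenarios leave out.* Suppose 15 of 20 ncMCE examinations are completed remotely and 5 only after someone enters the room, against MCE 20/20. CR as defined gives 15/20 v 20/20, P = 0.047. The shared components alone give 20/20 v 20/20, P = 1. Here the lower CR is a true shortfall of the non-contact system, and the shared-component comparison hides it.

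**The case against.** The strongest defence on CR is that contact belongs in the definition. ncMCE exists to avoid contact, the stated objective is its own feasibility, and no CR hypothesis or margin is set. All of that stands. A reader might infer that counting contact in one arm is an error to be removed, or that the plan commits to testing CR between arms. The documents support neither. The comparison follows only from a general rule in Chapter 8, in a sentence whose text is damaged.

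A reader might also infer that comparing arms on the shared components alone would be the fair replacement. It would not. Sections 4.2 and 4.3.2 rely on patients following verbal instructions to change position, so contact could occur because remote guidance failed. Step 4 shows the result.

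On blinding, Section 5.2 says "The evaluation of completion was made by another blinded researcher". It is tempting to conclude that this person cannot apply an item that exists in one arm only. But the section does not say what the researcher is blinded to, and contact could be recorded by someone else.

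On Section 6.4, it can be said that the wording is editorial and that a sensible investigator would follow 6.1.2. That limits the practical damage but leaves the sections in conflict.

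**Conclusion.** Both parts hold within limits. Section 6.4 is wrong as written: literally, it allows no related AE in the MCE arm and contradicts 6.1.1.1, 6.1.2 and its own timing condition. A reader might infer that the primary safety result is compromised; it is not, because that result counts AEs regardless of causality.

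The CR point is conditional on a between-arm comparison that the plan neither states nor rules out. If it is made, a lower ncMCE rate cannot be split into imaging and contact. False significance is unlikely at an assumed 10% contact rate (about 1-7%). The observed rates shift sooner: a gap of at least 10 points appears in 21-61% of trials, depending on imaging completeness and overlap, against 0-21% without contact. These figures rest on equal imaging in both arms and assumed contact rates. If no contact occurs, there is no effect.

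**What to change.** 1. In Section 6.4, replace ncMCE in all four grades with *the assigned system (ncMCE or MCE)*.
2. Keep CR as defined, contact included, as the primary feasibility estimate for ncMCE, with an exact 95% confidence interval. For scale, the Clopper-Pearson interval is 83.2-100% for 20/20, 68.3-98.8% for 18/20 and 50.9-91.3% for 15/20.
3. Beside it, not instead of it, report by arm the shared components: all six landmarks seen, and examination not discontinued.
4. For ncMCE, report the number of direct contacts (0/20 has an exact interval of 0-16.8%; 2/20 has 1.2-31.7%) and how many examinations were completed only after contact.
5. State in Chapter 8 that the shared-component comparison is not neutral by itself, because examinations completed with the help of contact count there as ncMCE successes.

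The cost is wording and a few reported figures, with no extra patients or visits. Section 5.1 does not name direct contact among the recorded items, so the case report form may need a line for it. The figures must be read together. Section 2.8 requires ethics approval before any change to the plan takes effect. Section 3.1 describes recruitment in the past tense, so if outcome data have already been seen, the added figures should be labelled post hoc.

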4.3.2 Secondary efficacy outcomes

Secondary endpoints included maneuverability score, pre-procedure perception and post-procedure satisfaction of patients, gastric examination time (GET), and diagnostic yield (DY). The maneuverability of the ncMCE system was evaluated with a questionnaire that consisted of signal transmission quality (stability and fluency), endoscopist comfort (strength needed to control joysticks and degree of fatigue), visualization of gastric mucosa (whether the mucus, foam in the stomach, and gastric fullness affected observation of gastric mucosa) and compliance of patients (patient ability to readily and correctly follow verbal instructions to change positions to assist in optimizing gastric views). The score for each index was 1 to 5, with 1 as the worst and 5 as the best, respectively, and a total ranging from 4 to 20. All patients were asked about the comfort and acceptability of the procedure using an improved pre-procedure perception and post-procedure satisfaction questionnaire, which was reviewed ease of swallowing, pain or discomfort experienced during and after the procedure, overall tolerability and convenience of the procedure, and knowledge, necessity for, and acceptability of ncMCE (Questionnaire 1) [18]. GET was defined as the time taken for gastric examination and determined using a digital stopwatch in the ESNavi software. DY or detection rate was calculated using the following formula: number of patients with positive findings divided by the total number of patients that underwent examination.

CHAPTER 5: DATA MANAGEMENT

5.1 Case report forms

The case report form is filled out by the researcher, and each enrolled case has one. After the completed case report form is checked by the clinical inspector, the first link is handed over to the data manager for data entry and management. CRF should include the patient's name, gender, age, identification (ID) number, phone number, address, diagnosis, clinical evaluation index, etc. During the study, the data of GET, maneuverability questionnaire, pre-procedure perception and post-procedure satisfaction questionnaire, diagnostic results, combined medication and AEs were recorded in the CRF.

CRFs will be treated as confidential documents and held securely in accordance with regulations. CRFs shall be restricted to the personnel approved by the Chief Investigator and recorded on the 'Study Delegation Log.' The investigator shall sign the CRF to confirm the accuracy of the data recorded.

5.2 Data collection

Information on the basic characteristics of the enrolled patients was collected prospectively. Each patient was followed up for 2 weeks by telephone and hospital information system to confirm capsule excretion and any adverse events (AEs), including COVID-19 infection. The maneuverability questionnaire for the endoscopist and improved questionnaire on pre-procedure perception and post-procedure satisfaction for patients were completed after the examination. To avoid systematic bias, a single endoscopist ([name]) performed each examination and made the diagnoses for all enrolled patients immediately. The evaluation of completion was made by another blinded researcher ([name]).

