Appendix 1.Comparison between ncMCE and MCE.

The capsule is 26.7 mm in length, 11.8 mm in diameter, and 4.5±0.5 g in weight, with a guidance magnet robot to control. The field of view is 140 degrees and the depth of view is 0 to 30 mm. After examination with an adaptive frame rate of 8 frames per second (fps), we got the image with 480×480 resolution.

	ncMCE	MCE
Data recorder	Sheet type	Vest type
Examination area	Two rooms	One room
System fixture	Guidance magnet robot Computer workstation with ESNavi software Endoscopic capsule; capsule locator Data recorder Remote control workstation Audiovisual exchange system	Guidance magnet robot Computer workstation with ESNavi software Endoscopic capsule; capsule locator Data recorder
PPE of endoscopist	Medical mask	N95 mask Isolation gown with water resistance Head cover Eye protection and face shield
Physical isolation	Yes	No

Appendix 2. Questionnaire 1 Improved questionnaire for pre-procedure perception and post-procedure satisfaction.

Pre-procedure Patient Perception

1. How anxious are you about the MCE/Nc-MCE?

4 = not at all; 3 = slightly; 2 = moderately; 1 = excessively

2. Do you expect any pain during the MCE/ ncMCE?

4 = not at all; 3 = slightly; 2 = moderately; 1 = excessively

3. How well do you know about Nc-MCE/the concept of Non-contact

4 = very well; 3 = well; 2 = ever heard but not know well; 1 = never even heard

Post-procedure Patient Satisfaction

4. How would you rate the swallowing/insertion of the instrument?

4 = very easy; 3 = easy; 2 = tolerable; 1 = difficult; 0 = very difficult

5. Did you experience pain during the procedure?

4 = none; 3 = minor; 2 = mild; 1 = severe; 0 = intolerable

6. Did you experience discomfort during the procedure?

4 = none; 3 = minor; 2 = mild; 1 = severe; 0 = intolerable

7. Did you experience pain after the procedure?

4 = none; 3 = minor; 2 = mild; 1 = severe; 0 = intolerable

8. Did you experience discomfort after the procedure?

4 = none; 3 = minor; 2 = mild; 1 = severe; 0 = intolerable

9. How would you rate the examination procedure?

4 = very comfortable; 3 = comfortable; 2 = tolerable; 1 = uncomfortable; 0 = very uncomfortable

10. If you would be given the possibility to select an examination for diagnosing your problem, would you choose this particular procedure?

4 = definitely yes; 3 = probably yes; 2 = maybe; 1 = probably not; 0 = definitely not

11. Rate the overall convenience of the test.

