4 = very convenient; 3 = convenient; 2 = not sure; 1 = inconvenient; 0 = very inconvenient

12. How much time did you miss from work or regular activities due to the test?

4 = 0-2 hours; 3 = 3-4 hours; 2 = 5-6 hours; 1 = 7-8 hours; 0 = >8 hours

13. Do you think it is necessary to perform nc-MCE during the outbreak?

4 = very necessary; 3 = necessary; 2 = not sure; 1 = unnecessary; 0 = very unnecessary

14. Do you think the Nc-MCE put you to any inconvenience?

4 = definitely not; 3 = not; 2 = not sure; 1 = yes; 0 = definitely yes

15. Rate the overall acceptance of the test.

4 = very acceptable; 3 = acceptable; 2 = moderate; 1 = acceptable only in special situations; 0 = unacceptable

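### Section 5.2 places the whole patient questionnaire after the examination, so the three pre-procedure items are, as written, retrospective; item 14 also does not fit the MCE arm

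*Combined protocol and SAP*

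**What the plan says.** Section 4.3.2 makes patient perception and satisfaction part of a secondary endpoint: "Secondary endpoints included maneuverability score, pre-procedure perception and post-procedure satisfaction of patients". The same section gives the form to both arms: "All patients were asked about the comfort and acceptability of the procedure using an improved pre-procedure perception and post-procedure satisfaction questionnaire".

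Section 5.2 states when the form is filled in: the "improved questionnaire on pre-procedure perception and post-procedure satisfaction for patients were completed after the examination". It names both parts and gives them one time point.

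Appendix 2 prints the form. Items 1 to 3 stand under the heading "Pre-procedure Patient Perception":

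- Item 1: "How anxious are you about the MCE/Nc-MCE"
- Item 2: "Do you expect any pain during the MCE/ ncMCE"
- Item 3: "How well do you know about Nc-MCE/the concept of Non-contact"

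Items 4 to 15 are the post-procedure part. Item 14 reads "Do you think the Nc-MCE put you to any inconvenience". It offers no MCE alternative and no not-applicable option.

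Section 3.1 says that patients learned their allocation only once baseline assessments were finished. It does not list those assessments.

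**The concern.** Taken as written, 5.2 has patients report their anxiety and expected pain once the procedure is over. By then they know their arm and how the examination went, and either may colour the answer. Item 3 is a knowledge question, but it too would be asked after ncMCE patients had just experienced the non-contact system. Chapter 8 plans between-group tests at two-sided P < 0.05. A difference on items 1 to 3 could therefore be reported as a difference in pre-procedure perception when it reflects the experience itself.

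Item 14 is a separate matter. An MCE patient has no ncMCE experience to report, so answers in the two arms do not measure the same thing. The documents give no scoring rule and no missing-item rule for this questionnaire, so an analyst has no guidance on what to do with the MCE-arm answers.

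**Working it through.** The plan states no figure to reproduce. The check compares the passages and counts items from the printed scales.

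**1. Is an earlier time given anywhere for items 1 to 3?**

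| Place | What it gives | Timing for items 1 to 3 |
|---|---|---|
| 3.1 | Baseline assessments before disclosure, not listed | None stated |
| 4.2 | The visit, from arrival to disinfection | No questionnaire step |
| 4.3.2 | Content and recipients of the form | None |
| 5.1 | Questionnaire data recorded in the CRF | None |
| 5.2 | Both parts of the form | After the examination |
| Appendix 2 | A pre-procedure heading over items 1 to 3 | Before, by label only; no slot |

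Only 5.2 gives a time, and it conflicts with the label in Appendix 2.

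**2. What would each possible time measure?**

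- Before disclosure of allocation: a baseline descriptor, with no arm difference expected beyond chance because allocation is random.
- After disclosure and before capsule ingestion: the reaction to the assigned procedure, where an arm difference is possible and interpretable.
- After the examination: recalled anxiety and expectation, mixed with the experience of the procedure.

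These are three different measurements. The text of 5.2 gives the third, while the endpoint's name requires the first or the second.

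**3. How much of the form is involved?**

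- Items 1 to 3 are scored 1 to 4 each. Their sum runs from 3 to 12, a range of 9.
- Items 4 to 15 are 12 items scored 0 to 4 each. Their sum runs from 0 to 48, a range of 48.
- All 15 items run from 3 to 60, a range of 57.
- If a total were formed, items 1 to 3 would carry 9 / 57 = 15.8% of its range.
- If the post-procedure items were summed, item 14 would carry 4 / 48 = 8.3% of that range. Leaving it out for MCE patients would give them 0 to 44 against 0 to 48 in the ncMCE arm.

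Both percentages depend on summing, which the documents do not specify for this questionnaire. They are shares of a scale and do not measure bias.

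**4. How many patients?** The plan is 40 patients at 1:1. The timing point touches all 40. Item 14 cannot be answered from experience by about 40 / 2 = 20 MCE patients.

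**5. Is item 14 the only such item?** Items 3 and 13 also refer to ncMCE. Item 3 asks about knowledge and item 13 asks for an opinion on its necessity, and a patient in either arm can answer both. Only item 14 presupposes having undergone ncMCE.

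**The case against.** The strongest reply is that 5.2 is loose drafting. A two-part form can be called complete once its second part is done, and the heading and forward-looking wording in Appendix 2 suggest that items 1 to 3 were meant to come first. They may even have been among the unlisted baseline assessments in 3.1. That is possible, and for this reason the finding concerns the text and does not assert what was done. But the reply leaves the time of part of a secondary endpoint unstated, and a reader still could not say which of the three measurements was taken.

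It can also be said that the consequences are small. The trial is a pilot without a sample-size calculation, no analysis is specified item by item, and any gap on item 3 may be slight because ncMCE was explained to both arms at consent. All of this stands, and it limits the weight of the point. It does not remove the conflict between 5.2 and Appendix 2.

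Finally, a form handed over during the preparation wait could be awkward in the ncMCE arm, where preparation is guided remotely (4.2) and direct contact counts as a technical failure (4.3.1). This is a fair caution about that slot. It does not apply to the baseline slot.

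**Conclusion.** The concern holds. As written, 5.2 turns three items labelled pre-procedure into recalled or post-exposure answers in an open-label comparison, and item 14 does not suit the MCE arm. The extent is 3 of 15 items in all 40 patients, and 1 of 12 post-procedure items in about 20. The direction and size of any bias cannot be derived from the documents.

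The timing part assumes that 5.2 is followed literally. If items 1 to 3 were in fact asked earlier, it reduces to a missing statement of when. The item 14 part needs no such assumption. Completion rate and adverse events, the primary endpoints, are not affected. The plan should be corrected on both points, but neither threatens its main conclusions.

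**What to change.** - **Timing.** Amend 5.2 so that items 1 to 3 are completed before the examination and items 4 to 15 after it. State the slot for items 1 to 3: (a) with the baseline assessments, before allocation is disclosed; or (b) after disclosure and before capsule ingestion. The investigators should choose according to what the endpoint is meant to show.
- **If the forms are already complete.** If items 1 to 3 were asked afterwards, label them as recalled, report them descriptively and do not present them as pre-procedure data. If they were asked earlier, one sentence in 5.2 saying when is enough.
- **Item 14.** Refer to the examination the patient had, or analyse the item in the ncMCE arm only.

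The cost is one form split into two sittings and one item reworded, with no extra visit or procedure. Slot (a) uses the existing baseline step in 3.1. Slot (b) could use the 40-minute interval between gastric preparation and ingestion in 4.2, provided that allocation has been disclosed by then and the form can be completed in the ncMCE arm without direct contact.
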